(4) Integration of Information (Fact-finding Phase): Because most safety problems are not unique to a particular nursing unit or hospital, the SAFE Loop Team integrates information from incident reports, follow-up investigations, and internal and external sources, including an AHRQ PSO.

(5) Feedback to Nurses (Mitigation Phase): To demonstrate that reports are used and can drive system changes, the SAFE Loop Team provides feedback about medication safety problems and mitigation plans.

[figure not shown]
Implementation of Intervention on an Individual Nursing Unit:

Engagement Phase (4 weeks):

Obtain Input: Nursing units convene daily huddles with their staff to discuss various issues. For three weeks, the SAFE Loop Team will attend one huddle per week to provide information on local safety events and obtain input on problems that frontline nurses believe to be common, severe, and preventable.

To include nurses who work at night and on weekends, the intervention will be disseminated through nursing huddles, which occur at shift change. We will also place fliers approved by the Marketing Dept on tack boards in common areas like break rooms and conference rooms away from public areas.

Select Target Medication Events: Each study nursing unit will select its own unique event. Through discussions with nurses and the SAFE Loop Team, the Unit Manager will choose a medication safety problem with a narrow enough scope to facilitate mitigation through targeted actions (e.g., problems

with opioids). The SAFE Loop Team will define inclusion/exclusion criteria for the unit's Target Medication Event.

Fact-Finding Phase (12 weeks):

Train Nurses: The SAFE Loop Team will train nurses to: (1) submit reports on Target Medication Events (in addition to usual reports); (2) focus on unsafe conditions and near misses, and (3) write detailed narrative descriptions of circumstances they observed leading up to each event. The SAFE Loop Team will train Nursing Unit Managers in a just-culture approach (i.e., addressing system issues rather than blaming individuals).

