6.3 MEASURES TO MINIMIZE BIAS: RANDOMIZATION AND BLINDING

Random Sequence Generation, Allocation Concealment, and Blinding: A researcher (not on the SAFE Loop or Data Collection teams) will use computer-generated random numbers to randomly assign the 4 nursing units within each of the 5 randomization blocks to one of 4 study groups, reflecting 2 arms (intervention and control) and 2 periods of time (sequential implementation; see Table below). Next, the researchers will place lists of the nursing units assigned to each group in opaque, sealed envelopes labeled with group numbers. At the start of each implementation period, the SAFE Loop Team will open the corresponding envelopes to determine the 5 nursing units that are assigned to each group. Research staff involved in data collection will be blinded to which nurses and patients are assigned to which arm.

Table: Study Design, Including Study Arms and Measurement Periods								
Group	½ Year 1		Year 2			Year 3		
1	Baseline	b	SAFE Loop	f	i	Follow-on		
2	Baseline	b	Control	f		Follow-on		
3			Baseline	b	SAFE Loop	f	i	Follow-on
4			Baseline	b	Control	f	Follow-on	
Light green = baseline measurement periods for Aims 1 & 3								
Orange = baseline (b) and follow-up (f) survey deployments for Aim 2								
Dark blue = SAFE Loop arm								
Medium blue = control arm								
Yellow = qualitative interviews (i) on implementation and follow-on period								
Dark green = follow-on period for Aim 3								

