B. Data Collection: Cedars-Sinai routinely surveys staff every two years using the Hospital SOPS. For the study, we will survey ~1980 eligible nurses on study nursing units twice via 4 total deployments of the full Hospital SOPS during two-week intermissions between study periods (Section 3A). To identify eligible nurses, we will obtain staffing databases including names, email addresses, title/position, percent effort, dates of work on the unit, and work schedule. At least 85% of nurses on study units will be eligible. Two weeks before deployment, we will send email notices to expect the survey and a researcher will visit nursing units to reinforce survey completion. The survey will be delivered via REDCap using a weblink embedded in an email. During each deployment, we will deliver the survey three times. We will incentivize completion at the individual (lotteries for iPads) and unit levels (gift baskets of snacks for response rates >65%). To minimize detection bias, the survey will not refer to the SAFE Loop intervention. To avoid having incomplete outcome data, we will monitor survey response rates and make adjustments to procedures as needed.

Methods for Aim 3: Rates of Target Medication Events

A. Measures: The primary outcome will be the *rate per 1,000 patient-days of Target Medication Events (preventable plus potential adverse drug events)* selected by the 10 nursing units in Groups 1 and 3. We will also examine the rate of events involving harm. We will define events as in prior research (**Table 10**).^{38,61,62}

Table 10: Medication Event Definitions		Examples
ADE (NCC MERP severity E-I)	A patient injury* resulting from a medical intervention related to drug(s).	A rash due to an antibiotic.
Preventable	An adverse drug event due to a medication error. †	A rash due to an antibiotic given despite known allergy.
Non-preventable	An adverse drug event not due to an error.	A rash occurring after first exposure to an antibiotic.
Potential ADE	A medication error that had the potential to cause injury but did not.	
Intercepted (NCC MERP B)	A medication error that was detected and stopped before the patient received the medication.	A pharmacist filling orders discovers a known allergy and prompts the prescriber to switch antibiotics.

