Non-intercepted (NCC MERP C-D)	A medication error in which the patient received the medication but did not to experience harm.	A patient with a known allergy to an antibiotic receives the drug anyway but does not develop a rash.

*An injury is an unintended consequence of care that negatively affects a patient's health and/or quality of life. † A medication error is an error anywhere in the process of drug ordering, dispensing, administration, and monitoring.

Descriptive Measures: We will characterize event severity/harm (NCC MERP categories), medication class (e.g., cardiovascular, diabetes, etc.), and route of administration (intravenous, oral, etc.). We will classify any errors by stage in drug therapy (ordering, dispensing, administering, monitoring), profession(s) involved (physician, pharmacist, nurse, other), and error types (allergy, drug-disease interaction, drug-drug interaction, drug-lab interaction, duplicate therapy, therapeutic omission, concentration, duration, route/dosage form, dose/frequency/rate, wrong medication, wrong patient, wrong timing, incomplete order).^{5,6,38,61} We will assess which events are Target Medication Events used by Group 1 and 3 nursing units (yes, no; and which unit).

B. Data Collection: The nursing units will implement mitigation plans designed to prevent Target Medication Events toward the end of the SAFE Loop implementation (Section 2B), which means that medication events will not start to fall until after that. Accordingly, we will monitor medication events during a baseline period, the implementation period, and 6-month follow-on period after implementation (Section 3A). To identify medication events, we will randomly sample 1,520 hospitalizations divided equally between the four study groups and the baseline and follow-on periods. (We will exclude the emergency department from Aim 3).

To detect medication events, we will employ the widely accepted Trigger Tool Method by Institute for Healthcare Improvement. It involves two stages: (1) nurses systematically screen medical records for “triggers” (clues that an event occurred) and write synopses of possible events, and (2) physicians review synopses to confirm and classify them. Many studies have used these methods, including studies by Dr. **[name]**.^{5,6,38,61-64}

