9.2 SAMPLE SIZE DETERMINATION

Aim 1:

On average per 6-month study period, each unit will provide 7,362 patient-days of care (294,470 pt-days/20/2) and submit 16.6 reports (665 reports/20/2). *H1.1.* The baseline rate is 2.26 incident reports per 1000 patient-days (665 reports/294,470). *H1.2.* Based on prior studies, the expected baseline number of system plus

Table 1: Minimum Detectable Difference in Outcome				
Implementation trend	Betw-Cluster Coeff. of Variation			
	0.01	0.05	0.10	0.20
1.1. Incident Reports per 1000 Patient-days				
Yes	1.241	1.277	1.392	1.851
No	0.794	0.815	0.877	1.115
1.2. System plus Human Factors per Incident Report				
Yes	0.471	0.481	0.515	0.651
No	0.299	0.305	0.322	0.391

human factors is 0.70 per report.¹ **Table 1** presents the minimum detectable differences in outcomes as functions of the between-cluster coefficient of variation (CV) and the presence of implementation trend, using two-sided t-tests for Poisson rates with 80% power at 5% significance level. These differences would be meaningful to safety leaders, reflecting >35% increases in reporting rates and enhanced detection of the multiple contributing multiple factors that are typically involved in every error.

Aim 2:

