Assessment of Survey Measurement Properties: To evaluate the two selected composite measures' internal consistency, we will calculate Cronbach's α using data from baseline survey. To assess construct validity and convergent validity, respectively, we will evaluate associations (Pearson correlation coefficients) between scores on the composite measures and: (1) the full Hospital SOPS, and (2) incident reporting rates at the nursing unit level. To assess responsiveness, we will compare scores from baseline and follow-up surveys among nurses in the SAFE Loop arm (paired t-tests). If the composite measures do not demonstrate good internal consistency, construct, and convergent validity, we will use the full Hospital SOPS.

Statistical Analyses: We will compare changes over time between study arms for Feedback and Communication About Error and Frequency of Events Reported. Multivariable Normal regression models will be fitted for both endpoints and we will test hypotheses similarly to Aim 1. We will adjust for nurse characteristics from the AHRQ survey: years working in this hospital, years worked in current nursing unit, and hours worked per week. We will perform subgroup analyses by years of experience in current profession, because experience has been associated with medication error rates.⁵⁹

Aim 3 Analyses:

Descriptive Analysis: We will calculate rates of preventable ADEs and potential ADEs per 1,000 patient-days, both overall and for the Target Medication Events for the Group 1 and 3 nursing units. We will describe the severity of the events, medication classes, errors, clinicians involved, and stages in drug therapy.

Statistical Analysis: We will compare changes over time between study arms for rates of (a) Target Medication Events per 1000 patient-days and (b) harmful Target Medication Events per 1000 patient-days. Multivariable Poisson models will be fitted with response variable as the number of (a) target medication events and (b) harmful medication events, with offset the length of stay divided by 1000

days. We will test hypotheses similarly to under Aim 1. Model covariates will include patient demographics, biological sex, Elixhauser comorbidity index, and insurance payer.

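### Target Events that define H3.1 are chosen by SAFE Loop units only, straight after their Aim 3 baseline and partly on perceived frequency, so regression to the mean can bias the estimate towards SAFE Loop

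*Combined protocol and SAP*

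**What the plan says.** **How and when the event is chosen.** Section 6.1.1 puts the choice in a four-week Engagement Phase at the start of the SAFE Loop period. Huddles are used "to provide information on local safety events and obtain input on problems that frontline nurses believe to be common, severe, and preventable". Then "the Unit Manager will choose a medication safety problem with a narrow enough scope to facilitate mitigation through targeted actions". The roles table in the same section lists this choice among the added SAFE Loop duties, and Section 8.1 (Aim 1) counts ten targets from ten SAFE Loop units. Control units therefore have none.

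**What is measured.** The Aim 3 primary outcome is the rate of Target Medication Events "selected by the 10 nursing units in Groups 1 and 3" (Section 8.1, Aim 3 Measures). The study design table in Section 6.3 places each group's baseline just before its SAFE Loop or control period; its key reads "Light green = baseline measurement periods for Aims 1 & 3". For chart review the team will "randomly sample 1,520 hospitalizations divided equally between the four study groups and the baseline and follow-on periods".

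**How it is tested.** Section 9.4.2 (Aim 3) states: "We will compare changes over time between study arms for rates of (a) Target Medication Events per 1000 patient-days". The test follows Aim 1, which is an interaction between study arm and time period.

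Nothing in the plan separates the information used for the choice from the baseline period, has control units nominate an event, or mentions regression to the mean.

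**The concern.** An event type picked partly because it has lately been frequent on a unit will, on average, have run above its long-run rate in the period that prompted the pick. If that period is also the baseline, the rate later drifts down with no intervention. Only one arm makes such a pick, so the control arm has no matching fall, and the arm-by-period contrast counts the difference as effect. In expectation the bias favours SAFE Loop or is nil.

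Randomization does not protect against this, because the selection comes after it and in one arm only. Blinded chart review does not either: reviewers would correctly count a real but temporary excess. More charts would only estimate the inflated baseline more precisely.

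What is at stake is how H3.1 is read. It is the trial's primary evidence on patient safety, and a fall in Target Events would be open to this second explanation.

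**Working it through.** **1. The plan's own figures.** 0.50 per 1,000 × 294.470 thousand patient-days = 147 events a year, as Section 9.2 says.

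The minimum detectable differences follow the cluster formula for rates,

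(m − 1)·d² = (1.960 + 0.842)²·[(λ0 + λ1)/y + k²(λ0² + λ1²)],

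with m = 10 units per arm (no trend) or 5 (trend). With the stated 2.26 reports per 1,000 and y = 7.362, and with 0.70 factors per report and y = 16.6, all 16 cells of Table 1 reproduce within 0.001.

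Section 9.2 gives no baseline rate for Aim 3. Fitting the eight H3.1 cells of Table 3 with λ1 = λ0 − d gives λ0 = 5.95 and y = 38.0, again within 0.001. The value 38 equals 1,520 / 40, the charts per unit and period. With y = 7.362 the first no-trend cell would be 1.132, not 0.516. So 5.95 per 1,000 patient-days is an assumption, and the exposure unit behind Table 3 needs confirming.

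**2. Size under strong count-based selection.** Section 9.2 gives the exposure: "On average per 6-month study period, each unit will provide 7,362 patient-days of care". Spread evenly over ten targets, 5.95 / 10 × 7.362 = 4.38 events per target, unit and half-year. Suppose the unit picks the problem with the highest half-year count among J candidates. Excess = (expected baseline count − expected long-run count) / 7.362.

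| Candidates J | Equally common: baseline count | Spurious fall | Excess per 1,000 | Unequal (gamma, CV 0.5): excess | Unequal (gamma, CV 1.0): excess |
|---|---|---|---|---|---|
| 3 | 6.17 | 29% | 0.24 | 0.17 | 0.10 |
| 5 | 6.91 | 37% | 0.34 | 0.25 | 0.16 |
| 10 | 7.84 | 44% | 0.47 | 0.35 | 0.24 |

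When candidates truly differ in frequency, the pick is more often a truly common problem, and the fall drops to 9–26% (0.10–0.35 per 1,000).

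**3. Weaker selection.** A wider simulation used 5 to 20 candidates, random weight for severity and preventability, half-year variation (CV 0 to 0.3), and beliefs resting 30% to 100% on the baseline half-year. At 0.6 events per 1,000 per problem, close to the fitted rate, it gave 0.07 to 0.47. Over assumed rates of 0.2 to 1.0 it gave 0.06 to 0.61. If beliefs rest only on long-run experience, the fall is 0.

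**4. Which definitions are scored.** Section 8.1 records whether an event is a Target Event and for which unit, but not whether the model scores each unit on its own event or on all ten. The absolute excess is the same either way. As a share of the unit's scored rate, in the wider simulation it is 2% to 50% if only the own event counts and about 0.6% to 12% if all ten do.

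**5. Against sampling error.** Assume about 4.9 days per chart: (294,470 − 19,108 emergency department patient-days) / (49,000 + 7,700 inpatient and observation encounters) = 4.86. Each arm and period has 1,520 / 4 = 380 charts, so 380 × 4.86 ≈ 1,850 patient-days and 5.95 × 1.85 ≈ 11 target events. The Poisson-only standard error of the contrast is √(4 × 5.95 / 1.85) ≈ 3.6 per 1,000. A bias of 0.24 to 0.47 adds 0.4 to 0.9 events to one cell and is 0.07 to 0.13 standard errors. Two-sided type I error rises from 5.0% to about 5.1–5.2%. Between-unit variation would make the relative effect smaller still.

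**The case against.** The strongest case against is that the text does not say units choose what was common in the baseline half-year. A reader might infer this from the timing, but Section 6.1.1 sets no look-back window. It speaks of what nurses believe, it names severity and preventability beside frequency, and the manager must also keep the scope narrow. Its examples read as standing system problems. Selection and outcome also use different sources: Section 8.1 takes events from chart triggers and the pharmacists' Ivents database, not from regular incident reports. A hospital-wide surge scored on the same definitions would regress in both arms.

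All of this stands, and it lowers the expected size, possibly to zero. It does not remove the mechanism. The sampled charts come from the same half-year, so they carry any real unit-specific excess that prompted the choice, and nothing in the plan keeps that half-year's events out of the huddles.

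A second tempting reading is that H3.1 would often be falsely positive. Dividing the smallest no-trend entry in Table 3 (0.516) by 2.80 gives a standard error of 0.184, and a bias of 0.24 to 0.47 would then put the error rate at about 26% to 72%. The documents do not support this. It treats the fitted exposure of 38 as thousands of patient-days per unit and period, when Section 9.2 gives an average of 7.362 thousand even if every chart were read.

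The plan does report overall preventable and potential ADE rates beside the target rates, so a fall in targets alone would be visible. That comparison is descriptive only and has no prespecified role in reading H3.1.

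**Conclusion.** The concern holds as a conditional bias. The documents establish the one-sided choice, its timing after allocation and directly after baseline, the use of local event information, and the lack of any safeguard. They do not establish how far the choice follows the baseline half-year.

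The size therefore runs from nil to about 0.35–0.47 per 1,000 patient-days under strong count-based selection, against the 0.50 the plan calls meaningful. The upper figures assume 5.95 target events per 1,000 patient-days, an even spread over ten targets, and choice by the highest half-year count; 0.47 also needs ten equally common candidates.

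At the planned chart count this is small against sampling error. It is a bias in the estimate and in its interpretation more than a large rise in type I error. It should be fixed because the remedy is cheap, but it does not by itself invalidate H3.1.

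**What to change.** 1. **Move the baseline charts.** State the window of local events presented at the Engagement huddles, and draw the Aim 3 baseline charts from the half-year before that window, in both arms and at the same number. Aim 3 data are collected retrospectively (Section 5.5), so this amends sampling dates only. The cost is that baseline sits about six months further from follow-on, equally in both arms. It reduces the bias rather than guaranteeing its removal, because nurses' beliefs may reach further back. Restricting what nurses are shown is not part of the remedy: it would change the intervention and could not confine their beliefs to a window.

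2. **Prespecify an outcome that neither arm selects.** Beside H3.1, fit the same arm-by-period Poisson model to all preventable plus potential ADEs. These are already classified, so no new data are needed. The price is that an effect limited to the targets is diluted.

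3. **Add a sensitivity analysis that drops each SAFE Loop unit's own Target Event.** It also removes much of the intended effect, so it serves interpretation and does not replace H3.1. State in advance that a fall confined to units' own targets will be read with caution.

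4. **Clarify two points in the same amendment:** which definitions are scored in which units, and the baseline rate and exposure unit behind Table 3.

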6.1.2 DOSING AND ADMINISTRATION

Not applicable

6.2 PREPARATION/HANDLING/STORAGE/ACCOUNTABILITY

Not applicable

6.3 MEASURES TO MINIMIZE BIAS: RANDOMIZATION AND BLINDING

Random Sequence Generation, Allocation Concealment, and Blinding: A researcher (not on the SAFE Loop or Data Collection teams) will use computer-generated random numbers to randomly assign the 4 nursing units within each of the 5 randomization blocks to one of 4 study groups, reflecting 2 arms (intervention and control) and 2 periods of time (sequential implementation; see Table below). Next, the researchers will place lists of the nursing units assigned to each group in opaque, sealed envelopes labeled with group numbers. At the start of each implementation period, the SAFE Loop Team will open the corresponding envelopes to determine the 5 nursing units that are assigned to each group. Research staff involved in data collection will be blinded to which nurses and patients are assigned to which arm.

Table: Study Design, Including Study Arms and Measurement Periods								
Group	½ Year 1		Year 2			Year 3		
1	Baseline	b	SAFE Loop	f	i	Follow-on		
2	Baseline	b	Control	f		Follow-on		
3			Baseline	b	SAFE Loop	f	i	Follow-on
4			Baseline	b	Control	f	Follow-on	
Light green = baseline measurement periods for Aims 1 & 3								
Orange = baseline (b) and follow-up (f) survey deployments for Aim 2								
Dark blue = SAFE Loop arm								
Medium blue = control arm								
Yellow = qualitative interviews (i) on implementation and follow-on period								
Dark green = follow-on period for Aim 3								

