4 STUDY DESIGN

4.1 OVERALL DESIGN

We plan to conduct a single-site cluster RCT of 20 acute care nursing units in the main Medical Center to compare use of the SAFE Loop (intervention nursing units) and an existing incident reporting system (control nursing units). Implementation of the intervention will be sequential in two phases (5 intervention and 5 control units will be randomized at a time). Randomization will occur in blocks to assure the similarities of the nursing units, with 4 nursing units per block, matched on patient population, size of the nursing unit, and other factors.

Corresponding to three study Aims above, outcome measures include:

- (Aim 1) incident reporting practices (rates at which nurses report high-priority medication incidents and numbers of contributing factors described per report),
- (Aim 2) nurses’ attitudes toward incident reporting (AHRQ Hospital Survey on Patient Safety Culture™, particularly perceptions of feedback and communication about error and of the frequency with which events are reported), and
- (Aim 3) rates of high-priority medication events (determined via IHI Trigger Tool method of medical record review).

Analyses will compare changes in outcomes between from before to after implementation in intervention and control arms. Qualitative interviews of nurses the SAFE Loop intervention arm will provide insight into implementation.

To minimize bias while also facilitating study feasibility, randomization will be done at the nursing unit level, and research staff involved in data collection will not have access to information on which nurses and patients were assigned to which arm. Also to minimize bias, nurses participating in the survey in Aim 2 will be informed that the results will be analyzed as part of a study on patient safety and incident reporting, without specifically linking the survey to the SAFE Loop study.

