5 STUDY POPULATION

5.1 INCLUSION CRITERIA

Study Nursing Units:

The study will include 34 acute care areas within Cedars-Sinai medical Center, which are grouped together into 20 nursing units by virtue of sharing the same nursing unit manager (**Table**). To facilitate blocked randomization, we grouped similar nursing units together into 5 blocks with four nursing units per block. The four nursing units within each block are as similar as possible (e.g., medical units are grouped together, ICUs are grouped together, etc.).

Table: Study Nursing Units, Patient Populations, Type, Size, & Allocation to Blocks						
	Unit Areas	Typical Patient Population	Type	Nurses	Pt-Days*	
Block 1: Larger medical floor units						
A	4SE, 4SW	Adult oncology	Floor	118	22,322	
B	5NE, 5NW	Cardiology	Floor	116	21,534	
C	5SE, 5SW	Adult medicine, gastroenterology	Floor	103	22,025	
D	7SE, 7SW	Adult medicine	Floor	92	22,025	
Block 2: Smaller medical floor units and emergency department						
A	6SE, 6SW	Congestive heart failure	Floor	104	18,552	
B	ED	Emergency department (ED)	ED	167	19,108	
C	3-SCCT	Medicine, congestive heart failure	Floor	50	10,188	
D	3NW	Short stay medical	Floor	41	2,437	
Block 3: Surgical floor units						
A	6NE, 6NW 6ICU	Kidney & liver transplant, cardiac surgery, Post cardiac-catheterization recovery	Floor, ICU	122	21,493	
B	7NE, 7NW	Med/surg orthopedics	Floor	106	20,901	
C	8SE, 8SW	Med/Surg bariatrics, GI surgery	Floor	100	15,230	
D	8NE, 8NW	Neurosurgery, Med/surg spine	Floor	78	15,230	
Block 4: Adult intensive care units						
A	4N-SCCT, 6-SCCT	Cardiac ICU, Cardiothoracic surgery ICU	ICU	130	10,711	
B	5-SCCT	Surgical and trauma ICU	ICU	91	6,381	
C	7-SCCT	Respiratory/medical ICU	ICU	69	7,085	
D	8-SCCT, 4NW	Neurosurgical ICU, Adult stroke/medicine	ICU, Floor	124	17,424	
Block 5.1: Obstetric and postpartum units						
A	3NE	Maternal-fetal care (obstetrics)	Floor	123	14,486	
B	3SE, 3SW	Post-partum	Floor	115	13,476	
Block 5.2: Pediatric units						
C	4S-SCCT, 4NE	Pediatric and congenital cardiac ICU, Pediatrics	ICU, Floor	44	3,903	
D	4NICU	Neonatal ICU	ICU	87	9,959	
*Patient-days of care on nursing unit per year.				Total	1980	294,470

Nurses:

- Aims 1 & 3 (SAFE Loop Incident Reports and Medical Record Review): All 1,980 nurses on the nursing units will be eligible to participate in the SAFE Loop and therefore participate in Aims 1 and 3.

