⁵ Audigier, V., White, I., Jolani, S. Debray, T., Quartagno, M., Carpenter, J., van Buuren, S. and Resche-Rigon, M. Multiple imputation for multilevel data with continuous and binary variables. Statistical Science 2018;33(2):160-183

⁶ Resche-Rigon, M. and White, I. R. Multiple imputation by chained equations for systematically and sporadically missing multilevel data. Statistical Methods in Medical Research 2018; 27(6): 1634-1649

⁷ White IR, Royston P, Wood AM. Multiple imputation using chained equations: Issues and guidance for practice. Stat Med. 2011 Feb 20;30(4):377-99.

Aim 3:

Table 3 presents the minimum detectable difference in event rates as functions of between-cluster coefficient of variation and implementation trend using a two-sided t-test for Poisson rates with 80% power at 5% significance level. A difference of 0.50 events per 1000 patient days is clinically meaningful, representing the avoidance of 147 events and 116 harmful events per year hospital-wide.

Table 3: Minimum Detectable Difference in Outcome				
Implementation trend	Betw-Cluster Coeff of Variance			
	0.01	0.05	0.10	0.20
3.1 Target Event Rate				
Yes	0.766	0.929	1.292	2.108
No	0.516	0.631	0.886	1.474
3.2 Harmful Event Rate				
Yes	0.322	0.335	0.373	0.486
No	0.220	0.230	0.257	0.340

Qualitative Interviews:

Qualitative methods do not involve statistical tests or rely on calculations of statistical power. Instead, we provide a rationale for the proposed sample size and describe analytical methods.

After SAFE Loop implementation, we will conduct one-on-one in-person interviews with 10 Nursing Unit Managers and 22 frontline nurses. This sample size will enable us to perform purposive sampling to acquire broad representation by randomization block (there are 5 blocks), study group (there are four groups, with five nursing units per group – one from each block; half of the groups receive the intervention), and nursing unit (there are 10 nursing units that will be randomized to the SAFE Loop arm). Thus, we will interview one nurse manger and two nurses from each study nursing unit, about 6 per block, and 16 per group.

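### Block 5 holds two labelled pairs of units (5.1 and 5.2), but the stated assignment rule does not use them, so one allocation in three puts each pair wholly in one arm

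*Combined protocol and SAP*

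**What the plan says.** Section 4.1 describes blocks "with 4 nursing units per block, matched on patient population, size of the nursing unit, and other factors". Section 5.1 repeats the aim: "To facilitate blocked randomization, we grouped similar nursing units together into 5 blocks with four nursing units per block". It then claims, of the result, that "The four nursing units within each block are as similar as possible".

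The table in section 5.1 gives four blocks a single title each. The fifth appears under two: "Block 5.1: Obstetric and postpartum units" (units A and B) and "Block 5.2: Pediatric units" (units C and D). The letters run from A to D as in the other blocks.

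Section 6.3 gives the assignment rule: "randomly assign the 4 nursing units within each of the 5 randomization blocks to one of 4 study groups". These four groups come from crossing arm with implementation period. Groups 1 and 3 receive the SAFE Loop; Groups 2 and 4 are controls. Section 9.2 confirms the layout: "there are four groups, with five nursing units per group – one from each block; half of the groups receive the intervention". The 5.1 and 5.2 labels are not mentioned outside the table.

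**The concern.** The sub-headings show that the planners recognised two patient populations inside Block 5. The rule in 6.3 treats the four units as interchangeable. If both maternity units fall in one arm and both pediatric units in the other, this block contributes a comparison of populations as well as of reporting systems.

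Comparing change from baseline removes stable level differences between unit types. Two things remain:

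- **Trends.** The models in 9.4.2 have an arm-by-period interaction, implementation step, random effects for nursing units, and patient or nurse covariates. They list no block term and no block-by-period term, so a trend specific to maternity or pediatric care would count towards the arm effect.
- **Target Events.** The Aim 3 primary outcome counts events chosen by the ten SAFE Loop units. Section 6.1.1 lets each unit choose its own event and lets a population define it. If both units of a kind receive the SAFE Loop, up to two of the ten events may concern patients for whom Block 5 supplies no control unit. Events that occur on all units, such as opioid problems, would be less affected.

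**Working it through.** **Inputs (table in section 5.1; group definitions in 6.3)**

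| Unit | Sub-block | Nurses | Patient-days per year |
|---|---|---|---|
| A: maternal-fetal | 5.1 | 123 | 14,486 |
| B: post-partum | 5.1 | 115 | 13,476 |
| C: pediatric/cardiac ICU, pediatrics | 5.2 | 44 | 3,903 |
| D: neonatal ICU | 5.2 | 87 | 9,959 |

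SAFE Loop = Groups 1 and 3; control = Groups 2 and 4. Step 1 = Groups 1 and 2; Step 2 = Groups 3 and 4.

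**The plan's own figures.** The table sums to 20 units, 1,980 nurses and 294,470 patient-days. With one unit per group from each of 5 blocks, each group has 5 units. All agree with the plan.

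**Count of allocations.** Four units to four groups, one each: 4! = 24, equally likely if no restriction applies. Classify by the two groups that the 5.1 pair occupies. Each class has 2 group pairs × 2 orders of A and B × 2 orders of C and D = 8 allocations.

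| Groups held by the 5.1 pair | Arms | Steps | Allocations |
|---|---|---|---|
| {1,3} or {2,4} | same | different | 8 |
| {1,2} or {3,4} | opposite | same | 8 |
| {1,4} or {2,3} | opposite | different | 8 |

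P(5.1 pair in one arm) = 8/24 = 1/3; check: 2/C(4,2) = 2/6 = 1/3. When the 5.1 pair shares an arm, the 5.2 pair must fill the other. These are one event, so the chance that either pair is unsplit is 1/3 and not 2/3. The 5.1 pair is in SAFE Loop in 4 of 24 and in control in 4 of 24.

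**Size of the imbalance within Block 5**

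- Pairs not split: A+B v C+D = 27,962 v 13,862 patient-days; 238 v 131 nurses.
- Pairs split: A+C v B+D = 18,389 v 23,435 patient-days (167 v 202 nurses), or A+D v B+C = 24,445 v 17,379 patient-days (210 v 159 nurses).

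The unsplit allocations are therefore also the worst for size, the second matching factor named in 4.1.

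**After splitting each pair between arms.** The second and third classes remain: 16 allocations, with P(pair in one arm) = 0. Each still puts one Block 5 unit in each group. Fix one unit in one group: its partner has 2 opposite-arm groups and the other two units have 2 orders, so 2 × 2 = 4 of 16. Each unit keeps a 1/4 chance of each group.

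**Share of the trial.** Block 5 is 4 of 20 units (4 of 19 in Aim 3, which excludes the emergency department) and 41,824/294,470 = 14% of patient-days.

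**The case against.** The strongest reply is that 6.3 does not say that every permutation is allowed. Only Block 5 carries sub-headings, and an intended paired restriction is a plausible reason for them. A reader might infer that the planners decided against using the sub-blocks; the documents do not show that. They are silent, and 1/3 is the chance under the rule as written. The reply stands as a reason to state the rule, but a restriction that appears nowhere cannot be relied on.

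Second, 5.1 promises only the best available similarity, and other blocks are mixed too: Block 2 contains the emergency department and a short-stay unit, and Block 4 an ICU combined with a floor. That is fair. Block 5 differs because the table already draws the subdivision that would help.

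Third, a reader might infer that the assignment is invalid or biased. It is not. It is proper randomisation, the unsplit outcome is equally likely in either direction, and the covariates and unit effects limit level differences. The documents give no evidence that trends differ between maternity and pediatric units, so no bias can be put in figures.

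Fourth, a reader might go further and require each pair to share a step as well as be split by arm, on the ground that every comparison would then be like with like. The table does not support that: 5.2 pairs a neonatal ICU with a combined pediatric ICU and floor of less than half its patient-days, and 5.1 pairs maternal-fetal with post-partum care. That rule would also tie population to step in this block in all 8 of its allocations, against 8 of 24 now. Under 9.4.2, results are presented by step if the three-way interaction is significant.

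**Conclusion.** The point holds as an inexpensive improvement to the design. Under 6.3 as written there is a 1/3 chance that arm coincides with population throughout Block 5. The consequence is possible confounding by trend, and by population-specific Target Events, in 4 of 20 units. It is a chance imbalance of limited reach; it neither invalidates the randomisation nor undermines the blocking elsewhere. The 1/3 assumes that all 24 allocations are equally likely. If a paired restriction was applied without being written down, the risk is already 0 and only the text needs correcting.

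**What to change.** State in 6.3 that, within Block 5, each of the 5.1 and 5.2 pairs is divided between SAFE Loop and control, and draw at random from the 16 allocations that satisfy this. Sealed envelopes and one Block 5 unit per group are unchanged.

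Costs: a small change to the allocation program, and 16 possible allocations in one block in place of 24. There is also some loss of concealment. In 8 of the 16, Step 1 takes one unit from each pair, and anyone who knows the rule can then deduce the arms of the two remaining units. All units are already in the trial, so this cannot affect which units enter.

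Also requiring each pair to share a step (8 allocations) is optional. It makes within-step comparisons closer and avoids that predictability, but ties population to step in this block. Choose one rule and record the reason.

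If allocation has already been done, state whether 5.1 and 5.2 were used and report which Block 5 unit went to which group. If the pairs were not split, add a sensitivity analysis of the primary outcomes without Block 5. It would rest on 16 units (15 in Aim 3), so its intervals would be expected to be wider.
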